## **Research Protocol : A Skill-Based RCT for Physical Activity Using Peer Mentors**

### **I. Objectives/Aims of the Study:**

The long-term goal of this study is to positively impact the physical activity patterns to improve health outcomes including the high rates of obesity in Appalachian teens. For this RCT, we will train peer mentors to deliver the culturally appropriate intervention and provide social support that is critical for facilitating and sustaining health behavior change. Our objective is to compare the efficacy of an innovative healthy lifestyle skills mentoring program (*Mentored Planning to be Active [MBA]*) to a teacher led program (PBA) for increasing physical activity in Appalachian high school teens. Our specific aims are:

**Aim 1:** Compare the efficacy of peer-led delivery (**MBA**) to teacher-led delivery (**PBA**) on health outcomes.

- a. Examine the relationship between health behaviors (sugar sweetened beverage consumption, sleep patterns, and health outcomes (body mass index, body fat at baseline)

**Aim 2:** Compare the efficacy of peer-led delivery (**MBA**) to teacher-led delivery (**PBA**) on physical activity behavior outcomes of Appalachian teens.

**Aim 3:** Examine the behavioral impact of the mentoring approach on teen mentors and teachers.

**Aim 4:** Examine the usefulness, ease of use, general satisfaction, and suggested refinements of the approach by the teen mentors and teachers.

**AIM 5:** Determine if self-regulation skills and exercise self-efficacy mediate the relationship between health outcomes and moderate/vigorous physical activity.

### **II. Background and Rationale:**

#### **Background**

Rural Appalachian populations have poorer health and fewer positive health-related behaviors compared to other United States populations. Appalachians are the most sedentary population in the U.S., and teens are particularly sedentary. Only 13.6% of adolescents reported 60 minutes of daily moderate activity, while 38% reported no moderate physical activity in the past week and 78.2% reported no vigorous physical activity in the past week. Obesity prevention through improving physical activity is a top priority in Rural Healthy People 2020. The prevalence of obesity among Appalachian teens exceeds national rates and is greater than 25%.

In academic underperforming schools such as those prevalent in Appalachia, the primary educational focus is to meet core academic mandates. To meet academic mandates, despite school-based health education and physical education programs, most Appalachian schools no longer require health and physical education. Low rates of physical activity and high rates of obesity persist in Appalachia. Efforts to improve physical activity in school-aged adolescents residing in Appalachia have relied on organized sports and school-based curricula delivered by teachers. These approaches have not been effective for Appalachian teens. One explanation may be **unique circumstances** present within Appalachia. Opportunities to participate in organized sports are limited due to inadequate school resources, lack of available transportation, and limited availability of school teams. As a result, most adolescents residing in Appalachia are unable to participate in organized sports. Further, school-based health interventions are limited in their scope and impact on obesity prevention. School-based interventions typically deliver content as part of a regular course such as health or physical education via teachers in classroom settings (this is the proposed comparison intervention). Low efficacy of these programs may be due to unique cultural challenges: a preference for informal sharing of information among local residents rather than health content delivered by formal teachers. Rarely do adolescent obesity prevention programs use peer mentoring. Though school-based interventions increase health knowledge, there is less evidence of the effectiveness for health behavior changes leading to **obesity prevention**. Longer-term follow-up of health behavior and health status outcomes in intervention studies are lacking.

#### **Rationale**

*Planning to be Active* (PBA) is a theory-based program for promoting regular physical activity in high school teens in Appalachia. In pilot studies, PBA was delivered by classroom teachers and showed efficacy in producing short-term increases in physical activity. Additionally, the research team has developed and tested a peer mentoring program based upon similar theoretical constructs used in PBA to successfully promote daily physical activity changes in Appalachian youth. Building upon these successes and our experience in this highly vulnerable population, we propose to expand the PBA intervention to be delivered in an after school program by trained high school mentors from Appalachia. We predict that peer mentors will be more effective than classroom teachers and will improve their own health behaviors, providing a double-edged intervention. Employing high school mentors as agents of change further addresses a unique need of Appalachian residents who often lack access to or trust in health professionals.

### **III. Procedures:**

#### **A. Research Design**

Our approach is to randomize participants to one of two groups: (1) intervention: Peer Mentoring (MBA), and (2) comparison: Teacher-Led (PBA). We will test the hypothesis that, compared to delivery by teachers in a classroom setting (usual care), an innovative delivery format of PBA by local peer mentors (trained 11th and 12th grade teens) will promote the adoption of healthier physical activity and regular exercise among 9th and 10th grade teens not engaged in organized sports by combining (a) peer mentoring by trained high school students to younger adolescents with (b) a tailored self-regulation lifestyle program. We propose a **group-randomized controlled trial** (G-RCT) to evaluate mentored delivery of a school-based intervention to improve physical activity behaviors and health outcomes among high school students in Appalachian Ohio. G-RCTs are characterized by random assignment of identifiable social groups (rather than individuals) to study conditions, with measurements taken on members of those groups to assess the impact of the intervention.

Prior to the intervention (baseline data), we plan to complete a sub-analysis of the relationship between health behaviors from lifestyle behavioral scale (sleep patterns reported and sugar sweetened beverage consumption rates and measured body mass index and body fat percentage).

#### **Sample**

We conducted a careful analysis of sample size calculations for primary analysis of the primary outcome: BMI in adolescents at 6 months post intervention. As discussed further below, we will use a mixed model ANCOVA in our primary analysis. Power calculations for this approach are given by Murray. Power in a G-RCT is influenced by five factors: number of groups (schools), number of individuals in each group (adolescents in each school), similarity of outcomes within clusters (school-level intra-class correlation [ICC] for BMI), similarity of outcomes within individuals (correlation of BMI measurements on the same student over time), and percentage of the variance that can be explained by the regression model. Using data from the **Ohio Family Health Survey**, we estimate that the school-level ICC for BMI among 9th graders in Appalachian Ohio counties is 0.023. We further estimate the over-time correlation of BMI measurements is 0.70 and that adjusting for age and gender will explain approximately 30% of the variance in BMI. With these assumptions, 10 schools per condition, and 75 students per school, we will have 82% power to detect a modest intervention effect (0.2 standard deviation difference between groups). This effect size would correspond to a difference in mean BMI between groups of 1.04 kg/m^2 if the observed variation in BMI is similar to that of all Appalachian 9th graders from the Ohio Family Health Survey (mean BMI = 23.41, SD = 5.2).

With an average of 75 mentee participants per school (50% participation rate of eligible students based on our preliminary work), we estimate that a total of 1,500 9th and 10th grade participants will be recruited over 2 years (750 per year). Further, 190 older teens will be recruited to serve as peer mentors (19 per school x 10 schools) in the MBA condition, for a study total of 1,690 high school-aged children. Recruitment of mentor and mentee participants will occur during the start of the school year (September).

At the end of the academic year, we will randomly select at least 1 PBA teacher and 5 teen mentors from each school that delivered the curriculum that year to participate in cognitive interviews. These semi-structured interviews will be conducted individually and will be audio-recorded. Audio recordings will be transcribed verbatim. Each interview will last approximately 30 minutes and will be held in a private room at each school.

## **Participant Recruitment and Retention**

Nine school districts from 9 rural Appalachian Ohio counties have agreed to participate; an excess of 10 schools needed for Wave1. Wave 2 schools will be recruited during Year 1 of the study (with amendment to IRB protocol once letters of support are received). Peer mentors will be recruited based on interest in working with peers, supporting others, and striving to cultivate their own health-supportive behaviors. Eleventh and 12th graders attending the target high school at the study's start will be eligible to participate as mentors if they are not expected to move from the participating school before the conclusion of the study; can speak English; and are recommended by a teacher, school advisor, or counselor. Teens interested in serving as mentors will complete an application form; selection will be based on: study needs, motivation to serve, and recommendations. Teen mentors with a BMI (for age and gender) above the 85th percentile or below the 5th percentile at the start of the study will be excluded because of concerns about those not classified as having a healthy weight serving as role models for healthy lifestyle behaviors. These exclusionary criteria will be clear in recruitment materials so those excluded understand why. All teen mentors will attend the same school and reside in the same local community as study participants. Each peer mentor will be assigned up to 4 adolescents (2 per session; 2 possible sessions each week); we will recruit 19 peer mentors per school. We will attempt to match mentors and mentees by gender.

School health teachers at participating schools will provide the comparison delivery method. With approximately 25 students per classroom, we anticipate 3 classrooms to participate in each comparison school. Based on preliminary studies, an 80% retention rate is expected, resulting in 82.5% power to detect a modest intervention effect. To aid retention of subjects, monetary incentives at each data collection time-point and booster kits for use during the summer months will be provided. In addition, attendance will be taken at all sessions; the PI will contact all subjects missing a session within 48 hours.

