### C. Internal Validity

To avoid study bias, schools will be randomized for study condition (PBA or MBA). The primary analysis will follow intention-to-treat principles. Randomization carries the expectation that the study conditions will be equivalent at pretest with respect to known and unknown prognostic factors. As a result, removing randomized groups or members from the analysis runs the risk of tampering with this balance and introducing bias. Further, loss of one or more groups could create an unbalanced design at the group level and heighten the risk associated with heteroscedasticity in a G-RCT. Based on our previous research, we estimate that no more than 20% of members measured at pretest will be missing at posttest, although we will make every effort to obtain posttest data on all individuals, including those who stop attending the sessions. Multiple imputation is now widely regarded as an effective method for replacing missing data, and we will use this approach, adapted for use with a G-RCT. We will employ SAS PROC MI and SAS PROC MIANALYZE to implement these multiple imputation procedures. Advantages of this analysis are that it carries the nominal Type I error rate across a variety of conditions found in G-RCTs, it provides results that correspond to the standard ANCOVA,

except that the standard errors and *df* for fixed effects are constructed to reflect the extra variation and limited *df* due to the G-RCT design; it often has good power compared to the alternatives; and the analysis is simple to conduct and explain. The only disadvantage is that it provides results in the form of adjusted condition means rather than change scores; we do not consider this an important disadvantage.

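### Stated power rises from 82% with 75 recruited students per school to 82.5% after a 20% loss, so at least one figure, or the student number attached to it, is wrong as written

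*Combined protocol and SAP*

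**What the plan says.** Under III.A Research Design, the Sample section states: "With these assumptions, 10 schools per condition, and 75 students per school, we will have 82% power to detect a modest intervention effect". It defines that effect as 0.2 SD, or 1.04 kg/m² with an SD of 5.2. The inputs are a school-level ICC of 0.023, an over-time correlation of 0.70, and about 30% of BMI variance explained by age and gender.

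The same section treats 75 as an enrolment figure. It begins its recruitment estimate "With an average of 75 mentee participants per school" and arrives at 1,500 students, whom it says "participants will be recruited over 2 years (750 per year"). Participant Recruitment and Retention agrees: "With approximately 25 students per classroom, we anticipate 3 classrooms to participate in each comparison school".

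That later section then gives a second power, for an effect described in the same words: "an 80% retention rate is expected, resulting in 82.5% power to detect a modest intervention effect".

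C. Internal Validity repeats the expected loss ("we estimate that no more than 20% of members measured at pretest will be missing at posttest") and plans multiple imputation for it.

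**The concern.** The Sample section itself lists the number of students in each school among the determinants of power. Going from 75 to 60 students per school with nothing else changed must lower power, yet the printed figure goes up by half a point. No change in effect size, ICC, correlation or number of schools is mentioned between the two statements.

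Power at the expected retention is the figure that shows whether planned enrolment is enough. As printed, the reader cannot tell whether the trial has 82% at 75 and less at 60, or 82.5% at 60 and more at 75.

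**Working it through.** **Is 75 the recruited number?** 75 × 20 schools = 1,500; 750 per year × 2 years = 1,500; 3 classrooms × 25 = 75. All three are counts before loss. Retained: 75 × 0.80 = 60 per school.

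**Inputs from the Sample section.** d = 0.2 SD (0.2 × 5.2 = 1.04 kg/m²), g = 10 schools per condition, ICC = 0.023, over-time correlation r = 0.70, R² = 0.30.

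**Assumptions not in the documents.** Two-sided alpha 0.05; noncentral t with 2(10 − 1) = 18 df. Let fm and fs be the fractions of student-level and school-level variance left after adjustment, and m the analysed students per school. In SD units:

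Var(difference) = 2 × [fm × (1 − 0.023)/m + fs × 0.023] / 10

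noncentrality = 0.2 / √Var

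Only the first term contains m, and it grows as m falls. For any fm above 0, therefore, power is lower at 60 than at 75, whatever fs is.

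**Reproducing the 82%.** Two choices match it at m = 75:

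- fm = 2(1 − 0.70)(1 − 0.30) = 0.42, fs = 0.70: Var = 2 × [0.42 × 0.977/75 + 0.70 × 0.023]/10 = 0.00431, noncentrality 3.04, power 82.1%. At m = 60, power is 79.7%.
- fm = fs = 2(1 − 0.70) = 0.60: power 82.0% at 75 and 78.7% at 60.

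The factor 2(1 − r) belongs to change scores. The plan describes a mixed-model ANCOVA and says "it provides results in the form of adjusted condition means rather than change scores". The ANCOVA student-level factor is 1 − 0.70² = 0.51, or 0.51 × 0.70 = 0.357 if the 30% also applies. Since fs is undocumented, several values were run:

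| fm | fs | Power at 75 | Power at 60 | Fall (points) |
|---|---|---|---|---|
| 0.51 | 0.51 | 87.7% | 84.8% | 2.9 |
| 0.51 | 0.70 | 80.1% | 77.3% | 2.8 |
| 0.51 | 1.0 | 69.0% | 66.7% | 2.4 |
| 0.357 | 0.357 | 96.1% | 94.6% | 1.5 |
| 0.357 | 0.51 | 91.0% | 89.1% | 1.9 |
| 0.357 | 0.70 | 83.5% | 81.5% | 2.0 |
| 0.357 | 1.0 | 72.0% | 70.3% | 1.8 |

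(Falls are taken from unrounded powers.) The level depends heavily on fs; the direction never changes.

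**Taking each printed figure as exact in turn** (fix fm, solve for fs):

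- 82.0% at 75: power at 60 is 80.0% (fm = 0.357), 79.1% (0.51) or 78.6% (0.60). Over all fm from 0 to 1 it runs from just under 82.0% down to 76.5%. The shortfall against 82.5% is 82.5 − 82.0 = 0.5 to 82.5 − 76.5 = 6.0 points.
- 82.5% at 60: power at 75 is 84.5% (fm = 0.357, fs = 0.675) or 85.4% (fm = 0.51, fs = 0.567). Over all fm it runs from just above 82.5% to 88.2%.

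**Other test conventions.** Calibrated to 82% at 75, power at 60 is 78.2% to under 82.0% with a one-sided t test, and 77.0% to under 82.0% with a two-sided normal approximation.

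**Rounding.** Suppose the figure at 75 were 82.99%, cut to 82%. Power at 60 would then be 81.0% (fm = 0.357) or 80.1% (fm = 0.51). Reaching 82.45% at 60 needs fm below 0.10.

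**The case against.** The strongest reply is that there was one calculation, at 60 retained students, giving 82.5%, and that the Sample section dropped the decimal. The trial would then have the power it claims after loss, and the fault would be one of labelling. This is plausible and cannot be ruled out. It does not clear the text: the Sample section would still attach its figure to 75 students and say nothing about retention, so the student number would be the wrong item.

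A second reply is that the two powers might refer to different time points. The Sample section names BMI at 6 months post intervention, while D. Data Analysis says power was based on T2, which Table 5 places at 3 months. A different over-time correlation could then reverse the order. But neither power statement mentions a changed input, and only one correlation is given, so this is conjecture.

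Third, the plan does not rely on complete cases. C. Internal Validity says: "Multiple imputation is now widely regarded as an effective method for replacing missing data". Imputation could at most bring power back to the level at 75 per school; it cannot take it higher. It does mean that, if 82% at 75 is right, the overstatement under the planned analysis could be as small as 0.5 point.

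The objection that the 0.5 to 6 point range is wide also has force. Its ends need adjustment to explain all or none of the student-level variance, which does not fit r = 0.70. With factors of 0.357 to 0.60 the gap is about 2.5 to 4 points (82.5 − 80.0 = 2.5; 82.5 − 78.6 = 3.9).

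**Conclusion.** The point holds. As written, 82% at 75 per school and 82.5% at 60 per school cannot both be true for the same effect and inputs. This rests on direction alone and does not depend on the assumed alpha, sidedness or variance factors.

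The size does depend on them. With two-sided alpha 0.05, 18 df and complete cases, the 82.5% is overstated by about 2.5 to 4 points (outer bounds 0.5 to 6) if 82% at 75 is right. If 82.5% at 60 is right, the 82% understates power at 75 by about 2.5 to 3.4 points with the ANCOVA factors (84.5 − 82 and 85.4 − 82), and by at most 6.2 (88.2 − 82). The documents do not allow a choice between these. On the first reading, power after loss stays near 79% to 80% with factors of 0.357 to 0.60, so the practical effect is modest. The design and the primary test are not affected.

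**What to change.** Recompute power at 75 and at 60 analysed students per school, using one stated method that matches the planned mixed-model ANCOVA. State alpha, sidedness, degrees of freedom, the student-level and school-level over-time correlations, and how the 30% explained by age and gender enters. Correct whichever figure or student number proves wrong, and say beside each power whether it refers to recruited or retained students. Note that the 60-per-school value is a complete-case figure, and so conservative if imputation recovers information.

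The cost is one recalculation and one or two restated figures. No change to design, sample size or analysis is proposed, and no replacement power value is offered here because the documents do not determine one.

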#### **IV. Measurement/Instrumentation**

**Measures.** Our measures are comprised of items adapted from published studies and preliminary studies. All measures have been used with adolescents residing in rural or Appalachian settings and show acceptable psychometrics: internal consistency reliability  $\alpha$  of .75-.94; face validity, predictive validity, and content validity, and/or construct validity are established (See Table 1).

Table 1. Variables, Instruments, Reliability, Validity and Data Collection Times for the Teens

Variable from Theoretical Framework	Instrument/ Source of Data	Cronbach's Alpha	Type of Validity	Data Collection Times			Measure Used in Statistical Analysis
				Pre	3 mo	6 mo	
Demographics (potential covariates/moderators)	Demographic questionnaire	NA	NA	X			Item ratings/answers
Behavioral Outcomes	Healthy Lifestyle Behaviors Scale	.84 and ↑	Face, Content Construct	X	X	X	Total score on the Healthy Lifestyle Behaviors Scale
	Accelerometer Activity			X	X	X	7 days of daily activity
Behavioral Outcomes	Daily Lifestyle Patterns		Content, Construct	X	X	X	4-item questionnaire
Primary Health Outcomes	Body Mass Index, BMI%, Body Fat%	NA	NA	X	X	X	BMI, BMI%, Bio Electronic Impedance
Psychological Determinants	Physical Activity Outcome Expectations	.86-.97	Construct Predictive	X	X	X	Total Score on each of 8 sub-scales: relaxation, fitness, competition, social growth, social continuation, health Total Score
	Self-Efficacy for Physical Activity	85-.94	Predictive	X	X	X	
Self-Regulation	Self-Regulation for Physical Activity	.89-.95	Content and Construct	X	X	X	Total score on each 6 subscales: goal setting, self-monitoring, overcoming barriers, time management, self-reward, planned support
	Social Support	.75-.88	Face and Construct	X	X	X	Total Score
Environmental Determinants	Perceived Environment for Physical Activity	Test-retest (59%-74%)	Construct	X	X	X	Total score on each of 1 subscale: neighborhood

#### **Demographics**

**Demographic Questionnaire.** Participants and peer mentors will complete a demographic questionnaire with: age, birthdate, grade in school, gender, race and ethnicity, zip code, and household members.

### **Primary Health Outcomes**

**Body Mass Index (BMI):** The primary outcome of BMI will be computed by measuring height and weight for each participant. BMI measurement procedures are further described in [Appendix A](#). We propose actual BMI as the primary outcome because this is a long-term trial. BMI z-scores are widely used and recommended for cross-sectional comparisons because they take into account differences in age and gender that may confound those comparisons. Recently, however, several authors have cautioned against the use of BMI z-scores for research using longitudinal designs, citing concerns that their use could result in spurious differences between groups. One reason for this problem is that children at the extreme ends of BMI distribution require substantially greater changes in weight than their thinner counterparts for the same change in z-score. Because the BMI z-score curves were constructed using only data between the 3rd and 97th percentiles, the CDC recommends caution when using growth curves outside this range. Berkey et al. noted that the difference between z-scores reflect larger differences in BMI in older compared to younger children.

Using CDC guidelines by age and gender, we also will calculate BMI percentiles with healthy weight status is defined as between the 25th and 85th percentile; overweight status is defined as between the 85th and 95th percentile; and obese is defined as above the 95th percentile.

**Body Fat Percentage:** Body fat percentage readings will be obtained by a portable body electronic impedance (BEI) device. During each data collection cycle, two measures using BEI will be obtained. The average percentage from the readings will be recorded. Room will be a normal ambient temperature (about 72 F). Participants will lie supine on a mat with non-conductive surface, with arms and legs abducted at 30-45 degree angles from the trunk. Electrode skin sites will be cleansed with alcohol wipes prior to application. Two distal current-introducing introducing electrodes will be placed on the dorsal surfaces of the hand and foot proximal to the metacarpal phalangeal and metatarsal phalangeal joints, respectively. Two voltage-sensing electrodes will be applied at the pisiform prominence of the wrist and between the medial lateral malleoli of the ankle. BEI measurements will be taken in the morning hours and prior to engagement of MVPA for that day. Participants will be instructed to be normally hydrated and urinate within 30 minutes of test. See [Appendix A](#) for measurement procedures. BEI data will be adjusted for height to allow for the estimation of total body water (TBW), relating height/impedance to TBW. TBW will be converted to total fat-free mass (FFM) from which body fatness will be estimated using equation accounting for height, resistance in ohms, body weight in kg and age. See Appendix A for complete equations.

